2. OVERVIEW OF STUDY DESIGN

2.1. Study Design

The research design uses a prospective observational comparative cohort study of patients treated for MDR-TB in multiple countries included in the early adopter (WHO pilot) program. A case of tuberculosis is one in which a health worker (clinician or other medical practitioner) has diagnosed TB. MDR-TB is defined as TB caused by *Mycobacterium tuberculosis* resistant in vitro to the effects of isoniazid and rifampicin, with or without resistance to any other drugs. Patients are enrolled in the registry by their healthcare provider once the healthcare provider diagnoses a patient with MDR-TB (inception cohort for comparison) or decides to treat with BDQ (exposure cohort specifically identifying indication for use for BDQ). All patient follow-up data will be collected at each visit from the healthcare provider during the course of BDQ treatment and for an additional 24 months after the last BDQ dose unless the patient is lost to follow-up or has died. Similar follow-up will be conducted for MDR-TB patients not treated with BDQ. Two options are under evaluation for the recruitment of MDR-TB patients not treated with BDQ. The first option under consideration is to include patients who are eligible for BDQ, but refuse BDQ at sites where BDQ is available. The second

option under consideration is the use of a stepwise cluster wedge design to enroll patients at centers who would be eligible for BDQ, but do not have access. The method for selecting MDR-TB patients not treated with BDQ will depend on how BDQ is made available in the early adopter countries. All patients newly diagnosed and treated for MDR-TB will be eligible for inclusion in the registry. Additionally, all patients initiating BDQ treatment will be eligible for inclusion in the registry regardless of the indication for use. All patients meeting the inclusion criteria and providing informed consent for participation in the study will be enrolled. The registry enrollment period will be open for 36 months with an additional 24 months of follow-up for safety assessment. This enrollment period should allow the enrollment of approximately 3000 MDR-TB patients treated with BDQ.

Data will be collected in an observational manner such that the management of the patient is determined by the patient and the caregiver and not influenced by the registry protocol. The registry will describe care as it is provided.

Relevant Institutional Review Board (IRB)/Ethics Committee (EC) and Health Authority (HA) approvals will be secured prior to initiating the study.

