1.3. STUDY OBJECTIVES

1.3.1. Primary Objectives:

The following primary objectives were specifically chosen to address gaps in the currently available data informing BDQ benefits and risks:

- To describe the type of hospital or outpatient setting administering MDR-TB treatment
- To describe MDR-TB treatment delivery modalities, including treatment and management programs in place, administration of drug under closely monitored conditions, and consultation with experts in clinical management of MDR-TB and public health authorities such as national MDR-TB advisory groups within National TB Control Programs
- To describe the demographic and clinical characteristics of MDR-TB patients participating in the registry
- To describe MDR-TB treatment regimen utilization including dosages, duration, past treatment history, past medical history, concomitant medications used for conditions other than TB
- To measure adherence to WHO guidance in terms of selection of MDR-TB regimens and selection of patients for BDQ treatment

- To describe the indication for use of BDQ
- To measure extent to which patient informed consent is obtained for receipt of BDQ
- To describe BDQ and background drug susceptibility testing expressed as minimum inhibitory concentration (MIC) at baseline and for isolates from the last positive specimens
- To actively monitor adverse events using cohort event monitoring, including the monitoring for drug-drug interactions
- To actively monitor for mortality events using cohort event monitoring that includes collection of cause of death where available
- To estimate the relative risk of adverse events and mortality events by comparing event rates among BDQ-treated patients to respective event rates among patients not treated with BDQ, adjusting for potential imbalances in predictors of receiving BDQ for treatment, as well as predictors of mortality, assuming the availability of comparable populations
- To describe the following treatment outcomes separately for patients with MDR-TB and patients with non- MDR cases or MDR status not documented, as stipulated by the WHO revised definitions for resistant TB cases in 2013: cured, treatment completed, treatment failed, died, lost to follow-up, not evaluated, and treatment success
- To compare the treatment outcomes of cured, treatment completed, treatment failed, died, lost to follow-up, not evaluated, and treatment success between BDQ-treated patients and patients not treated with BDQ

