4.2.1. Exposure Definition and Measures

Exposure to MDR-TB regimens will be determined by documentation by the healthcare provider. The initiation date of MDR-TB treatment for each patient will be the drug initiation date as reported by the healthcare provider. The discontinuation date for each drug exposure will be defined as the date the drug was stopped as reported by the healthcare provider. Duration of exposure will be based on initiation and discontinuation dates for each drug. Switches from one drug to another will be captured and time on drug will be defined by the exposure periods.

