4.4.2.2. Analysis of Adverse Events

Incidence rates of adverse events will be calculated for the BDQ and non-BDQ treated cohorts. Additional descriptive analyses will include incidence rates of adverse events of interest for BDQ treated patients and non-BDQ treated patients calculated by dividing the total number of each adverse event by the total person-exposure time and expressed as the number of events per person-year, and 95% confidence intervals.

Relative risk rates and 95% confidence intervals will be calculated and appropriate stratified analyses will be conducted for each adverse event, including death. Poisson regression models will be used to adjust for potential confounders based on baseline clinical characteristics and patient demographics. Adjustments for imbalances between the treatment groups will be applied using accepted methods based on sample size availability and the observed overlap of key patient characteristics. If the sample size is adequate, propensity score methods may be used to adjust for imbalances between the 2 treatment groups before receiving the BDQ treatment or other MDR-TB therapy. Adjustment methods will be determined *a priori* to any comparative analysis with respect to safety outcomes.

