4.5. Evaluation of Appropriateness of Comparison Study

The evaluation of appropriateness of a comparison of BDQ-exposed patients with non-BDQ-treated MDR-TB patients will be based on the consistency of the clinical

experience of the 2 cohorts. This assessment will be conducted based on distribution of propensity scores for receipt of BDQ or other treatment regimens.

The evaluation of clinical experience will assess the patients' clinical and demographic characteristics in relation to receipt of BDQ and other MDR-TB regimens. Information will be captured on the patients' clinical and demographic characteristics that could be predictive of treatment appropriateness. This information will be incorporated into multivariate model to identify a group of patients with similar characteristics to the BDQ cohort but treated with other MDR-TB treatments. All patients will be assigned a propensity score ranging from 0 to 1 that represents the fitted probability of receiving BDQ. The scores from non-BDQ-treated patients will be plotted against those for BDQ-treated patients. Overlap in the cohorts based on sample size estimates of approximately 750 patients per treatment group in the propensity space must exist for a comparison of safety events between the two groups. An epidemiologist trained in propensity score estimation and matching methodology will make this assessment on the epidemiological validity of a comparison between the 2 treatment cohorts.

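### Comparison patients enter at MDR-TB diagnosis and BDQ patients at the BDQ decision, but the protocol sets no common time origin, no rule for later BDQ starters, and no MDR-TB restriction on the BDQ side of the safety comparison

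*Protocol*

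**What the plan says.** **Entry.** Section 2.1 gives two triggers for enrolment. The provider either "diagnoses a patient with MDR-TB (inception cohort for comparison) or decides to treat with BDQ (exposure cohort specifically identifying indication for use for BDQ". The same section adds that "all patients initiating BDQ treatment will be eligible for inclusion in the registry regardless of the indication for use".

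**Contrast.** A primary objective in 1.3 estimates relative risk by "comparing event rates among BDQ-treated patients to respective event rates among patients not treated with BDQ", with adjustment for predictors of receiving BDQ "as well as predictors of mortality, assuming the availability of comparable populations". A further objective compares the WHO treatment outcomes, death among them, on the same treated/untreated split. Section 4.4.2.2 states: "Incidence rates of adverse events will be calculated for the BDQ and non-BDQ treated cohorts".

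**Exposure.** Section 4.2.1 uses the start and stop dates of each drug: "Switches from one drug to another will be captured and time on drug will be defined by the exposure periods". Section 4.4.2.2 divides events by person-exposure time for the adverse events of interest, under additional descriptive analyses.

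**Outcome.** Section 4.2.2 defines the outcome of death, for MDR-TB cases, as death from any cause at any time during treatment. Section 4.4.2.1 estimates the treatment outcomes among MDR-TB patients separately by BDQ status, and describes BDQ use outside MDR-TB on its own.

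**Comparability.** Section 4.5 assesses "a comparison of BDQ-exposed patients with non-BDQ-treated MDR-TB patients" and requires propensity-score overlap of about 750 patients per group. Two ways to recruit comparators are under evaluation in 2.1. One is to "include patients who are eligible for BDQ, but refuse BDQ at sites where BDQ is available"; the other enrols BDQ-eligible patients at centers without access.

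**The concern.** A patient enrolled at diagnosis who starts BDQ some months later fits both cohort definitions. The registry takes in all newly diagnosed MDR-TB patients and all new BDQ patients at participating sites (3.1.1), so such patients are to be expected.

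If they are counted as BDQ-treated from enrolment, they must have survived to the first BDQ dose. Those who died while waiting are counted as comparator deaths. That makes BDQ look protective when it does nothing.

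Patients who first enter at the BDQ decision raise a different problem. Their follow-up starts later in the disease than that of comparators, so risk is compared at different distances from diagnosis. The direction depends on how risk changes with time and on who is selected for BDQ.

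Finally, section 4.2.2 lists drug-sensitive, latent, extra-pulmonary and non-tuberculosis mycobacterial indications as possible BDQ use. Non-MDR BDQ patients have no counterpart in a comparator made up only of MDR-TB patients. At stake are the mortality relative risk and the outcome comparison, both primary objectives.

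**Working it through.** The protocol gives no figure on this point to reproduce, so the check is a reading of the text and then an illustration.

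**Reading.** Three rules would close the gap.

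1. *A common time origin.* None is stated. Section 4.2.1 defines treatment start as a drug initiation date, but a patient who starts one regimen and later adds BDQ has two such dates.
2. *Allocation of pre-BDQ time and events.* Section 4.2.1 defines time on each drug. Neither it nor 4.4.2.2 says that time before the first BDQ dose counts as unexposed; it could equally be dropped. Treatment outcomes are proportions, so person-time does not enter them.
3. *Restriction to MDR-TB.* This is present for treatment outcomes (4.4.2.1). It is absent on the BDQ side for adverse events and deaths (4.4.2.2) and for the comparability check (4.5).

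**Illustration, with no true effect.** The 15% mortality comes from section 1.1.5, which gives no time horizon. The 24 months, the constant hazard, the share due to switch (50%) and the switch time s are assumptions.

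Hazard: λ = −ln(0.85)/24 = 0.00677 per month. Survival to s: S(s) = exp(−λs).

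Take 1,000 patients enrolled at diagnosis, 500 of them due to start BDQ at s if alive, classified ever/never from enrolment:

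- Ever-BDQ: deaths = 500 × (S(s) − 0.85); person-months = 500 × [s·S(s) + (S(s) − 0.85)/λ].
- Never-BDQ: deaths = 500 × 0.15 + 500 × (1 − S(s)); person-months = 500 × 0.15/λ + 500 × [(1 − S(s))/λ − s·S(s)].

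| | s = 3 | s = 6 |
|---|---|---|
| S(s) | 0.980 | 0.960 |
| Ever-BDQ deaths / person-months | 64.9 / 11,061 | 55.1 / 11,016 |
| Never-BDQ deaths / person-months | 85.1 / 11,091 | 94.9 / 11,135 |
| Rate ratio | 0.77 | 0.59 |
| Risk of death, ever / never | 0.133 / 0.167 | 0.115 / 0.183 |
| Risk ratio | 0.80 (0.795 unrounded) | 0.63 |

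With 25% to 75% due to switch, the rate ratio runs from 0.83 to 0.62 at 3 months and from 0.68 to 0.42 at 6 months. The risk ratio is the relevant measure for outcome proportions.

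**Other ways of handling the same data** (50% due to switch, constant hazard):

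- Pre-BDQ time dropped: 0.88 at 3 months, 0.79 at 6.
- Pre-BDQ time credited to unexposed: 1.00 at both.
- Two separate cohorts, each followed from its own entry: 1.00 at both.

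**Hazard not constant.** Suppose the hazard is doubled in the first 6 months, still with 15% mortality at 24 months. The later hazard is 0.1625/(2×6 + 18) = 0.00542 per month. A separate BDQ cohort entering at 6 months has that rate. Comparators followed from diagnosis have 0.15 deaths per 21.88 person-months = 0.00686. The ratio is 0.79 with no immortal time at all. Under the same hazard, time-varying BDQ without adjustment for time since diagnosis gives 0.63 (75% due to switch at 6 months). Within each band of time since diagnosis the two hazards are equal by construction, so adjusting for that time removes the bias here.

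**The case against.** The strongest reply is that an enrolment trigger is not an analysis time zero. Section 4.2.1 dates exposure drug by drug, and 4.4.2.2 uses person-exposure time and speaks of imbalances before BDQ or other MDR-TB therapy is received. Both point towards treatment start. Both comparator options require BDQ eligibility: refusers stand at the same decision point as acceptors, and patients without access cannot switch while access is lacking. The relative risk is conditional on comparable populations and on the overlap check, channeling is admitted in section 5, and a separate SAP is promised.

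Much of this stands. A reader might infer that the design builds immortal time into the relative risk. The documents do not support that: a patient who first enters at the BDQ decision accrues no immortal time before entry, no passage prescribes ever/never classification, and the exposure-period language points the other way. A reader might also take the ratios above as an estimate of the bias in this registry. They are not, because the protocol gives no switching share, delay or time horizon.

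What does not stand is that these provisions settle the matter. The person-exposure denominator is stated only for events of interest, and it does not place pre-BDQ time. The outcome proportions have no such protection. The propensity and Poisson adjustments use baseline characteristics, and an overlap check may reveal BDQ patients unlike any comparator, but neither fixes the time origin. The comparator options are undecided and set no index date. Entry events, eligibility, the contrast and the definition of death are protocol matters, so this is more than SAP detail.

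**Conclusion.** The concern holds in a limited form. The protocol pairs two different entry events with a treated/untreated contrast and leaves open both the time origin and the handling of diagnosis-cohort patients who later start BDQ. The exposure is greatest for death as a treatment outcome and for the mortality relative risk. It is smaller for adverse-event rates computed on exposure periods.

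The bias could be nil if pre-BDQ time is credited to the unexposed group and risk is steady over time. It could be sizeable (0.77 or 0.59 with no true effect) if patients are classed ever/never under the assumptions set out above. Differing entry times alone could give about 0.79 for a 6-month delay with a doubled early hazard. The missing MDR-TB restriction for adverse events and deaths follows directly from the text and rests on none of these assumptions.

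**What to change.** In 4.4.2.2, and for the comparison of treatment outcomes:

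1. Treat BDQ as a time-varying exposure. Time and events before the first BDQ dose count as unexposed. Treatment-outcome proportions by BDQ status can remain as description.
2. Adjust for time since MDR-TB diagnosis or treatment start, with covariates measured at the start of the regimen being compared.
3. Restrict the adverse-event and mortality relative risk to documented MDR-TB in both groups, say the same in 4.5, and describe other BDQ use separately, as 4.4.2.1 already does.

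The cost is protocol wording, some added programming and a small loss of non-MDR BDQ patients from the comparison. Drug dates are already collected (4.2.1), and time-varying variables are recorded at each visit (4.2.4). Matching every comparator to a BDQ start on time since diagnosis is not required; it could leave too few matches for the overlap of about 750 per group.

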4. STATISTICAL METHODS

4.1. Sample Size and Study Precision

The three year enrollment period of the registry is estimated to result in an enrollment of 3000 to 5000 BDQ-treated patients.

A cohort of 3000 patients gives a 95% probability of identifying an adverse event with an incidence rate of 1:1000.

Based on the sample size estimates below, a registry of 1000 BDQ-exposed patients would have 95% power to detect a Relative Risk of 2 assuming $\alpha = 0.05$ and a 1:1 ratio of BDQ-exposed patients to unexposed patients for events that occur with a frequency of at least 3%.

Power and Sample Size for Adverse Events Occurring with a Frequency of at Least 3%							
Exposed	Relative Risk						
	1.5	2	3	4	5	7	10
0	0.049985	0.049985	0.049985	0.049985	0.049985	0.049985	0.049985
100	0.133214	0.252768	0.559428	0.828643	0.961157	0.999754	1.000000
200	0.190756	0.414883	0.844041	0.986772	0.999721	1.000000	1.000000
300	0.243884	0.552078	0.952777	0.999299	0.999999	1.000000	1.000000
400	0.294233	0.663681	0.987120	0.999970	1.000000	1.000000	1.000000
500	0.342210	0.751574	0.996745	0.999999	1.000000	1.000000	1.000000
600	0.387925	0.819043	0.999224	1.000000	1.000000	1.000000	1.000000
700	0.431400	0.869774	0.999824	1.000000	1.000000	1.000000	1.000000
800	0.472639	0.907271	0.999961	1.000000	1.000000	1.000000	1.000000
900	0.511649	0.934588	0.999992	1.000000	1.000000	1.000000	1.000000
1,000	0.548449	0.954244	0.999998	1.000000	1.000000	1.000000	1.000000

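### The 95% power in Section 4.1 assumes independent patients and would not hold at 1000 per group under the stepped cluster comparator that Section 2.1 leaves open

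*Protocol*

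**What the plan says.** Section 2.1 lists two possible sources of patients not treated with bedaquiline (BDQ), both still being evaluated. The first is eligible patients who refuse BDQ at sites that have it. The second reads: "the use of a stepwise cluster wedge design to enroll patients at centers who would be eligible for BDQ, but do not have access". Which of them applies is left to depend on how the drug is rolled out.

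Section 4.1 contains one power table and one summary claim, "a registry of 1000 BDQ-exposed patients would have 95% power to detect a Relative Risk of 2". The stated conditions are alpha 0.05, a 1:1 ratio and an event frequency of at least 3%. The claim is not tied to either comparator source, and the sidedness of alpha is not given in words. The same section expects 3000 to 5000 BDQ-treated patients. No size is given for the untreated group.

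Section 4.5 sets a condition for making the safety comparison at all: "Overlap in the cohorts based on sample size estimates of approximately 750 patients per treatment group in the propensity space must exist". An epidemiologist then judges whether the comparison is valid.

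Section 4.4.2.2 plans Poisson regression adjusted for baseline clinical characteristics and demographics, with propensity scores if numbers allow. The protocol gives no ICC, design effect, number of centres, number of steps or period term.

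**The concern.** In a stepped wedge, centres move from no access to access at successive calendar steps. Untreated person-time then lies mostly early and treated person-time mostly late. An analysis has to remove calendar effects, which costs information even when patients within a centre are uncorrelated. Correlation within centres costs more. A power figure for independent patients does not carry over.

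The relative risk of adverse events and death is a primary objective (Section 1.3.1). If the wedge is adopted and Section 4.1 stands as written, a null result for an event near 3% would be read against a 95% chance of detecting a doubling that the design did not have at that size.

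**Working it through.** **Inputs from the protocol.** Section 4.1: 3%, read as the unexposed frequency; RR 2, hence 6%; 1000 per group; alpha 0.05; stated power 0.954244. Section 4.5: about 750 per group.

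**Step 1: reproduce the stated figure.** The table's row for zero exposed patients is 0.049985. This equals Φ(−1.645) = 0.049985, whereas 2Φ(−1.96) = 0.049996, so the table is one-sided. For independent patients,

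power = Φ{[(p1 − p0) − z·√(2p̄(1 − p̄)/n)] / √([p0(1 − p0) + p1(1 − p1)]/n)}, with p̄ = 0.045.

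- n = 1000, one-sided: (0.03 − 1.645 × 0.009271)/0.009247 = 1.595, power 94.5%. This is within a point of the table.
- n = 1000, two-sided: (0.03 − 1.96 × 0.009271)/0.009247 = 1.279, power 90.0%. This does not match the table.
- n = 750: 87.7% one-sided, 80.1% two-sided.

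The table is therefore sound for independent patients and a one-sided test.

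**Step 2: the same sizes under a wedge.** Assumed, because the protocol does not give them: a complete wedge with all-or-none crossover, equal cluster-periods, 20 to 60 centres, 4 to 6 steps, ICC 0 to 0.05. The Hussey-Hughes variance of the treatment effect, with I centres, T = steps + 1 periods and m patients per cluster-period, is

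Var = Iσ²(σ² + Tτ²) / [(IU − W)σ² + (U² + ITU − TW − IV)τ²],

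where τ² = ICC × p̄(1 − p̄) and σ² = (1 − ICC) × p̄(1 − p̄)/m. U is the number of treated cluster-periods. W is the sum over periods, and V the sum over centres, of the squared number treated.

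Example with 2000 patients in total, 20 centres and 5 steps: T = 6, m = 2000/120 = 16.67, p̄(1 − p̄) = 0.042975, U = 60, W = 880, V = 220.

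- ICC 0: σ² = 0.0025785. Var = 20 × 0.0025785/320 = 0.0001612, SE = 0.01270 and 0.03/SE = 2.363. Power is Φ(2.363 − 1.645) = 76% one-sided and Φ(2.363 − 1.96) = 66% two-sided. The variance for independent patients is 4 × 0.042975/2000 = 0.0000860, so inflation is 1.87.
- ICC 0.05: τ² = 0.0021488 and σ² = 0.0024496. Var = 0.0007516/(320 × 0.0024496 + 1120 × 0.0021488) = 0.0002356, SE = 0.01535 and 0.03/SE = 1.955. Power is 62% one-sided and 50% two-sided. Inflation is 2.74.

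Across 20 to 60 centres and 4 to 6 steps:

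| Per group | ICC | One-sided | Two-sided |
|---|---|---|---|
| 1000 | independent patients | 94.5% | 90.0% |
| 1000 | 0 | 74–78% | 63–67% |
| 1000 | 0.05 | 61–68% | 48–56% |
| 750 | independent patients | 87.7% | 80.1% |
| 750 | 0.05 | 51–59% | 39–46% |
| 3000 | 0.05 | 94–96% | 89–93% |

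A wider grid (12 to 48 centres, 2 to 6 steps, ICC 0 to 0.10) gives 48–78% one-sided at 1000 per group. No setting tried comes near 95%. The ICC 0 row needs no assumption about correlation: removing calendar effects alone is enough to break the claim.

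**Step 3: commoner events.** Section 1.1.5 cites deaths in 11% of treated MDR-TB patients. Take 11% versus 22%, 750 per group and an inflation of 2.9, near the top of the range for 20 to 60 centres. The effective size is 750/2.9 = 259 per group and SE = √(0.2695/259) = 0.0323. Two-sided power is Φ(0.11/0.0323 − 1.96), about 93%.

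**The case against.** The strongest reply is that the wedge is only a possibility, described in one clause. The protocol specifies no steps and no all-or-none crossover. Care is not to be influenced by the registry (Section 2.1), so treated and untreated patients could coexist in a centre once access begins. The inflation above then belongs to an assumed layout. This stands, and it is why the result must be a labelled range and not a corrected value. It does not rescue Section 4.1, whose claim is not limited to the other comparator source.

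A second reply is that centre and period terms are ordinary content for the separate statistical analysis plan announced in the Synopsis. That is fair for the model's details, and their absence alone would not be a finding. The 95% figure, however, is fixed in this protocol.

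A reader might infer three stronger things, none of which the document supports:

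- **That the power table is miscalculated.** It reproduces one-sided for independent patients. Part of the gap between 95% and any two-sided wedge figure is sidedness (94.5% to 90.0% at 1000 per group), not clustering.
- **That the 750 rule opens the comparison below a planned power.** Section 4.5 attaches no power to that number. It is a minimum overlap followed by a judgement of validity.
- **That the mortality comparison is underpowered.** At the protocol's own 11% mortality, a doubling keeps about 93% two-sided power at 750 per group even with inflation of 2.9.

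**Conclusion.** The point holds conditionally. Section 4.1 states 95% power without restricting it to a comparator source, and the figure is valid only for independent patients and a one-sided 5% test. Under a complete stepped wedge of the same size, on the like-for-like one-sided basis, it falls to roughly three quarters from calendar adjustment alone and to under 70% at ICC 0.05. These sizes rest on assumed centres, steps, ICC and crossover; the protocol supplies none of them.

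The loss matters for events close to the 3% floor. If about 3000 per group were available, most of it would be recovered, but the expected 3000 to 5000 are BDQ-treated patients only, so this cannot be relied on from the document.

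**What to change.** - **Section 4.1:** state whether alpha is one- or two-sided. State that the table and the 95% figure assume independent patients and do not apply to the wedge option.
- **If the wedge is chosen:** restate power as a range, with the assumed ICC, number of centres and number of steps labelled as assumptions. Do not write in a single power value from an unsourced ICC.
- **Section 4.5:** note that about 750 per group was not sized for clustering. Converting it to a fixed effective number is not advised: at inflation of 2.3 to 2.9 it would require 750 × 2.3 = 1725 to 750 × 2.9 = 2175 actual patients per group, on an ICC with no source.
- **Section 4.4.2.2 or the statistical analysis plan, for the wedge only:** fit the Poisson model with calendar-step terms and a centre random effect or centre-robust variance. Without them the intervals ignore clustering, and BDQ exposure is confounded with calendar time.

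The cost is a few sentences and a less favourable stated power for the wedge option. Enrolment does not change.
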